Chronic knee OA pain is influenced by systemic inflammation and metabolic factors such as poor diet, excess weight, and metabolic syndrome, which contribute to “meta-inflammation” through dysregulation of adipokines, cytokines, and lipids (Zhang et al. 2024 PMID: 38243159). A systematic review and meta-analysis of 73 studies show significant reductions in self-reported pain severity following nutrition interventions (Brain, K. et al. 2019 PMID: 30294938) and prebiotics may hold promise for the management of knee OA in adults with obesity (Fortuna, R. et al. 2024 PMID: 38713231). In addition, the endocannabinoid (EC) system plays a central role in pain regulation and emotional response to chronic pain (Woodhams, S. G., et al. 2015). PMID: 25846617). Prebiotic fibre supplementation may support gut health, reduce systemic inflammation, and improve biomarkers linked to OA and chronic pain, complementing the effects of exercise.

Emerging evidence links gut microbiome composition to OA-related knee pain, with studies indicating its role in pain intensity, progression, and sensitivity- including neuropathic pain - largely through inflammation modulation (Ding, W. et al. 2021 PMID: 32889847). Short chain fatty acids (SCFAs), produced by bacterial fermentation of dietary fibre, mediate many of the microbiome’s anti-inflammatory effects. However, the interactions between physiotherapy exercise, prebiotic

inulin supplementation, pain modulation, inflammatory biomarkers, and the gut microbiome remain poorly understood. Specifically, the effects of inulin and exercise on pain, microbiome composition, inflammatory markers, and circulating SCFA levels in individuals with knee OA have yet to be explored.

Rationale: This trial will adopt a 2x2 factorial design to assess the individual and combined effects of exercise and prebiotic inulin supplementation over six weeks. The study will evaluate their effect on knee osteoarthritis (OA) pain, as well as molecular and gut microbiome parameters.

STUDY OBJECTIVES

PRIMARY OBJECTIVE

1-To assess the magnitude of the effect of prebiotic supplementation (inulin) side by side with physiotherapy exercise versus placebo (maltodextrin) on knee pain

SECONDARY OBJECTIVES

1-To assess the combined effects of exercise and prebiotic inulin supplementation (synergistic effect) over six weeks

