The placebo and inulin groups will receive pre-measured pots containing either the supplement or placebo powder for each week, along with scoops. Participants will be instructed to take either 2 or 3 scoops daily, depending on whether they are in the inulin or placebo group. They will also be provided with guidance on incorporating their daily dose into their diet, such as mixing it into smoothies or using it as a topping on yoghurts and breakfast cereals. Participants will be asked to maintain a daily dietary compliance record to track their supplement intake, including any missed doses and the reasons for not taking the supplement. If participants experience adverse effects, such as severe bloating or nausea, that prevent them from continuing with the supplement, they will be instructed to notify a member of the study team.

After the six weeks of interventions, all participants will fill in the same questionnaires and perform the physical tests, to enable evaluation. Participants and the researcher will meet in person twice: once at enrolment and again six weeks later.

OUTCOMES

Primary outcome:

- Numerical Rate Score (NRS) for pain to assess changes in response to the interventions.

Secondary outcomes:

- Changes in markers of pain assessed by quantitative sensory testing, and in markers of inflammation
- Changes in gut microbiome composition and serum levels of short chain fatty acids (SCFAs) in response to the interventions.
- Changes in functional outcomes (e.g., 30 second sit to stand test, get up and go test)

STATISTICAL ANALYSIS PLAN

The clinical trial data will be analysed using the appropriate parametric and non-parametric statistical tests, we will compare outcome measures (such as pain sensitivity and pain ratings) between the exercise and non-exercise groups while adjusting for baseline scores.

Secondary analyses (i.e., correlations between changes in SCFAs and changes in pain measures) will be conducted using the appropriate type of statistical test based on data normality (e.g., Spearman's).

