A planned analysis of covariance (ANCOVA) will be conducted to assess differences in follow-up outcome measures among treatment groups while adjusting for baseline levels. The model will include treatment group (arm: inulin only, exercise only, inulin & exercise, control/placebo) as a categorical independent variable and baseline outcome scores as a covariate. Model assumptions will be evaluated through residual diagnostics to ensure the validity of the analysis

To further explore differences between groups, post hoc pairwise comparisons will be conducted, including comparisons between groups and an evaluation of potential interactions to assess potential synergy between treatments.

R studio and Graph Pad PRISM will be used for the statistical analyses.

SAMPLE SIZE AND JUSTIFICATION

Primary outcome is a Numerical Rate Score (NRS) for pain as used in our previous exercise intervention study (Gohir et al 2021 PMID: 33620447). The 2x2 factorial design with 30 individuals per block (total n=120) has 80% to detect differences of 0.51 SDs. In our own study delivering the exercise intervention the effect size observed was a drop of 0.84 SDs in the exercise arm compared with only 0.2 SDs in the control arm (who only received a leaflet). In addition, the study has adequate power to detect moderate main effects of inulin on pain outcomes, with 30 participants per group providing ~75–80% power to detect an effect size of Cohen's $d \sim 0.6$ at $\alpha = 0.05$. If changes in gut microbiome via dietary supplementation can achieve a difference of 0.51 or higher in NRS, the study is powered to detect them.

Secondary outcomes: a key goal of this study is to link changes in molecular markers in serum to changes in pain and other outcomes (n=120, 60 per arm for the 2x2 intervention). For instance, the effect sizes in changes in a circulating molecular pain modulator observed previously from 0.32 to 0.71 nmol/L; SD=0.61 after 6 weeks of inulin supplementation hence yielding an effect size of 0.62 STDs. It increased from 1.61-1.82 nmol/L; SD=0.31 yielding an effect size of 0.61 STDs with the exercise intervention.

DATA MANAGEMENT

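### The plan tests NRS pain in several ways without naming the deciding contrast or any error control, and it lists no inulin main-effect test although it powers for one.

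*Combined protocol and SAP*

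**What the plan says.** All references are to the combined protocol and SAP.

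- **OUTCOMES.** The primary outcome is the "Numerical Rate Score (NRS) for pain to assess changes in response to the interventions".
- **PRIMARY OBJECTIVE.** The aim concerns the effect of "prebiotic supplementation (inulin) side by side with physiotherapy exercise versus placebo (maltodextrin) on knee pain". This can be read as an inulin main effect, as the combined arm against placebo, or as two separate questions.
- **SECONDARY OBJECTIVES.** The combined (synergistic) effect is listed here, as the first item.
- **STATISTICAL ANALYSIS PLAN.** The section opens with a plan to "compare outcome measures (such as pain sensitivity and pain ratings) between the exercise and non-exercise groups while adjusting for baseline scores". It continues: "A planned analysis of covariance (ANCOVA) will be conducted to assess differences in follow-up outcome measures among treatment groups", with arm as a four-level factor and the baseline score as covariate. Then, as further exploration, "post hoc pairwise comparisons will be conducted, including comparisons between groups", together with "an evaluation of potential interactions to assess potential synergy between treatments".
- **SAMPLE SIZE AND JUSTIFICATION.** With 30 per cell (n=120), 80% power is claimed for 0.51 SD. A second sentence refers to inulin main effects, with 30 per group, d about 0.6 and power of about 75–80%. The 0.05 level appears only in this section, without sidedness.

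No section states a multiplicity method, a testing order, or a rule that pairwise tests depend on the arm test. None says which NRS result answers the primary objective. An inulin versus no-inulin comparison is not among the listed analyses.

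**The concern.** Several listed tests bear on the same primary outcome, and nothing says which one decides. This has two consequences.

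First, the deciding result could be picked after the data are seen. The false-positive risk then depends on a rule nobody has written down.

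Second, the listed tests do not match the question. The only margin named is exercise. An exercise effect alone can make the arm test and the combined-versus-placebo comparison significant. The contrast that isolates inulin with the whole sample, and that the power calculation appears to assume, is missing. A reader of the final report could not tell from the plan what result would have shown that inulin works.

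**Working it through.** **Inputs.** From the documents: four arms, 1:1:1:1, 30 per cell, n=120, alpha 0.05, 0.51 SD; earlier exercise study 0.84 SD versus 0.2 SD, so the exercise effect is 0.84 − 0.20 = 0.64 SD. Assumed: two-sided tests, normal outcomes with equal variance, no dropout, and a baseline–follow-up correlation r, which the documents do not give (0 and 0.5 where effects are present; 0.3 to 0.7 under the null).

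**1. The plan's own power figure.** Power ≈ Φ(d/√(2/n) − 1.96).
- Margin, 60 vs 60: 0.51/√(2/60) = 2.793; Φ(0.833) = 79.8% (t-test 79.1%). The stated 80% reproduces.
- Single pair, 30 vs 30: 0.51/√(2/30) = 1.975; Φ(0.015) = 50.6% (t-test 49.3%).

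So the 0.51 SD claim fits a main effect and does not fit any pairwise comparison.

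**2. Counting the listed tests.** Four arms give 4×3/2 = 6 pairs; the count is derived, not stated. Adding the exercise margin, the 3-df arm test and one interaction contrast makes nine tests. ANCOVA residual df = 120 − 5 = 115; critical t = 1.98.

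**3. Neither treatment works.** Chance of at least one p<0.05 on NRS, allowing for correlation between the tests:

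| Rule | Chance |
|---|---|
| Six unadjusted pairs (studentized range: P(q > 1.98×√2), 4 groups, 115 df) | 20.1% |
| Pairs + exercise margin + arm test | 20.8% |
| All of these + interaction | 21.5% |
| Pairs only after a significant arm test | 5.0% |
| Exercise margin or arm test (gated pairs add nothing) | 8.1% |
| Exercise margin, gated pairs, ungated interaction | 11.2% |

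Full ANCOVA simulation with r = 0.3, 0.5 and 0.7 gives 20.9% to 21.9% for the third row. Treating the nine tests as independent gives 1 − 0.95⁹ = 37%, which overstates the risk.

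**4. Exercise works (0.64 SD), inulin does nothing.** Simulated for r = 0 and r = 0.5:
- At least one listed inulin contrast (inulin vs placebo, combined vs exercise, interaction) falsely significant: about 11% at either r. Gating on the arm test leaves it at about 11%, because exercise alone usually opens the gate.
- Arm test significant: 84% (r=0) to 93% (r=0.5). For r=0 the non-centrality is 120 × 0.32² = 12.3, giving 83.6%.
- Combined vs placebo significant: 69% to 81%.

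The last two are correct rejections, since those means do differ. They carry no information about inulin.

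**5. Power for inulin if the two main effects decide** (0.51 SD, r=0): each at 5%, about 79%; Holm, about 78% if exercise works at 0.64 SD and about 70% if it does not.

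**The case against.** **The wording implies a ranking.** The ANCOVA is called planned, while the pairwise tests are called post hoc and introduced as further exploration. A reader may treat the arm test as a gate, which brings the null rate to 5%, or to about 8–11% with the exercise margin and an ungated interaction. The opening sentence on exercise may also be only a general description of that ANCOVA. This stands to the extent that 21% is an upper reading and should not be quoted without its conditions. It does not remove the gap: no gate is written, the ANCOVA is not named as decisive, and gating does not lower the 11% for inulin when exercise works.

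**The intended contrasts can be inferred.** The 80% reproduces only at 60 vs 60, main effects are mentioned in the sample-size text, and synergy is a secondary objective. This is fair evidence of intent. But the inulin test is still absent from the analysis section. The sentence on inulin main effects also quotes 30 per group: at d=0.6, 30 vs 30 gives 64% and 60 vs 60 gives 91%, neither of which is 75–80%.

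**A reader might infer that the 84–93% and 69–81% are false-positive rates.** They are not. They are power to detect a real exercise effect. The plan nowhere says that either result establishes an inulin effect; harm arises only if one is credited to inulin.

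**A reader might infer that adjustment across the two factors is obligatory.** The two main effects answer distinct questions, and testing each at 5% in a factorial trial is defensible.

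**Conclusion.** The point holds: the deciding NRS contrast is not named, error control is not stated, and the inulin main effect is powered for but not listed as an analysis.

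The size depends on the unstated rule. With no effect of either treatment, the chance of a false positive is about 21% if every test is unadjusted at two-sided 0.05 and any hit counts as an effect. It is about 5–11% if the pairs are gated on the arm test. The documents do not support a flat statement that one trial in five would report a false effect. In the scenario the group's own earlier study suggests, with exercise at 0.64 SD and inulin null, about 11% of trials give a false signal on a listed inulin contrast.

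These figures cover NRS only and assume 30 completers per arm and normal outcomes. The missing deciding contrast does not depend on any of them. It should be corrected before the data are analysed, because a choice made afterwards cannot be made good.

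**What to change.** In the STATISTICAL ANALYSIS PLAN section, state the following for NRS:

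1. The exercise and inulin main effects (60 vs 60 each), from one baseline-adjusted factorial model, decide the primary outcome. Define each as the average over the two levels of the other factor, so that it is the marginal contrast and not the effect in one arm pair.
2. The 3-df arm test and the combined-versus-placebo comparison are not evidence for inulin.
3. The interaction is reported as secondary, in line with the secondary objective on synergy.
4. The pairwise comparisons are supportive, with Tukey-adjusted p-values and confidence intervals (critical t about 2.61 in place of 1.98).
5. Either each main effect is tested at two-sided 5%, or the two are tested with Holm at an overall 5%; say which.

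The PRIMARY OBJECTIVE should be reworded to match.

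**Cost.** This is a change of wording, with no change to design or data collection. Testing each main effect at 5% keeps the planned power (about 79% at 0.51 SD). Holm costs about one percentage point for inulin if exercise works, but lowers power to about 70% if it does not, below the stated 80%. That trade-off is the sponsor's to make and record.

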- Are currently following or anticipated to commence a specialised commercially available weight loss diet and/or programme
- Pregnant or breastfeeding
- History or current psychiatric illness (including clinical depression)
- History or current neurological condition (e.g. epilepsy)
- Those undergoing revision, having severe hip OA, inflammatory arthropathies
- Diagnosed non-OA cause of knee pain (e.g. rheumatoid arthritis)
- Neuropathy or diabetes mellitus
- Having taken part in a research study in the last 3 months involving invasive procedures or an inconvenience allowance

RANDOMISATION AND BLINDING

Randomisation will be done using a computer-generated randomisation and allocation concealment software called “sealed envelope” (<https://www.sealedenvelope.com/>). At least thirty participants will be divided equally between the treatment arms. Blinding for the exercise intervention is not feasible at this stage since participants will be informed if they have been randomly assigned to one of the exercise groups. Because this might affect the motivation of

participants who were randomly assigned to the non-exercise arms, they will be offered access to the web-based exercise programme after completing the trial. Although it is challenging to blind exercise intervention studies, both the research examiner and the participants will be blind to the intervention and the food supplementation.

MATERIALS

Inulin fibre (20g) in powder form, maltodextrin (10g) in powder form, Joint Academy app, faecal sample kit, blood sample collection materials.

PHYSIOTHERAPY INTERVENTION

INSPIRE will use a web-based exercises platform known as Joint Academy (JA) as a previous RCT from our group demonstrated promising results for this platform (Gohir et al 2021 PMID: 33620447). The Swedish face-to-face self-management programme "Artrosskolan" (The Osteoarthritis School), which offered structured information and exercises for knee arthritis to a relevant population with the condition, served as the model for this programme. The JA company has granted permission for this study to be carried out using their digital platform.

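### The ~75–80% power stated for d ~0.6 is wrong on either reading (63% for 30 vs 30, 90% for 60 vs 60), and the target difference and target sample size are stated inconsistently

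*Combined protocol and SAP*

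**What the plan says.** All references are to the combined protocol and SAP.

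**Sample Size and Justification** makes three statements about power for the NRS pain score:

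- For the whole design: "The 2x2 factorial design with 30 individuals per block (total n=120) has 80% to detect differences of 0.51 SDs".
- For inulin, it claims that "the study has adequate power to detect moderate main effects of inulin on pain outcomes", supported by "30 participants per group providing ~75–80% power to detect an effect size" of Cohen's d about 0.6 at alpha 0.05.
- In closing, it says that if dietary supplementation "can achieve a difference of 0.51 or higher in NRS, the study is powered to detect them".

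The paragraph on secondary outcomes in the same section describes the factorial comparison as "n=120, 60 per arm for the 2x2 intervention".

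**Randomisation and Blinding** gives a different number: "At least thirty participants will be divided equally between the treatment arms".

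The section does not state sidedness, an SD for the NRS, an allowance for dropout, or a correlation between baseline and follow-up scores.

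**The concern.** In a 2x2 factorial trial with 30 per cell, the main effect of inulin compares the two inulin cells with the two non-inulin cells, 60 vs 60. A comparison of one arm with another is 30 vs 30. The inulin sentence attaches the cell size to the main effect. It also sits oddly beside its neighbour: if 120 participants give 80% power for 0.51 SD, the same contrast cannot have equal or lower power for the larger effect of 0.6 SD.

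The primary objective concerns the effect of inulin on knee pain, and this sentence is the plan's claim that the trial can detect it. The analysis plan fits treatment as a four-level factor and follows it with pairwise comparisons, which are 30 vs 30. A reader would take those comparisons to have 75–80% power.

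The other two inconsistencies affect the same basis. An NRS is scored in points, so 0.51 with no SD unit reads as about half a point. A floor of thirty participants could be met on paper while leaving the factorial design far too small.

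**Working it through.** **Inputs.** 30 per cell, 120 in total, effect sizes 0.51 and 0.6 SD, and alpha 0.05 come from Sample Size and Justification. The 1:1:1:1 allocation comes from Study Design. Two-sided testing is an assumption, tested in step 3.

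**Formula.** For n per group and standardised difference d, the noncentrality is d·√(n/2). Approximate power is Φ(d·√(n/2) − 1.96). The exact figure uses the noncentral t distribution with 2n − 2 degrees of freedom.

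**Step 1. Reproduce the plan's own 80% for 0.51 SD.** With 60 vs 60: 0.51 × √30 = 2.793, and Φ(2.793 − 1.96) = 79.8%. Noncentral t gives 79.1%. With 30 vs 30 the same difference has only 49%. The stated 80% is therefore an unadjusted, two-sided 60 vs 60 comparison. The difference detectable with exactly 80% power is 0.516 SD.

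**Step 2. Apply that convention to d = 0.6.**

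| Comparison | Noncentrality | Power (normal) | Power (t) | Plan |
|---|---|---|---|---|
| 30 vs 30 | 0.6 × √15 = 2.324 | 64.2% | 62.7% | ~75–80% |
| 60 vs 60 | 0.6 × √30 = 3.286 | 90.8% | 90.3% | ~75–80% |

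With 30 per group, 75% power needs 0.69 SD and 80% needs 0.74 SD. At d = 0.6, 75% and 80% power need about 40 and 45 per group.

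**Step 3. Look for one convention that gives both figures (t-based).**

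| Assumption, none stated in the plan | d = 0.6 (plan: ~75–80%) | 0.51 SD, 60 vs 60 (plan: 80%) |
|---|---|---|
| One-sided 0.05, 30 vs 30 | 74% | 87% (80% reached at 0.46 SD) |
| ANCOVA, baseline correlation 0.5, 30 vs 30 | 75% | 89% |
| ANCOVA, baseline correlation 0.6, 30 vs 30 | 81% | 93% |
| Attrition leaving 40–45 per margin | 75–80% | 62–67% (on the same retained numbers) |

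For ANCOVA, d is divided by √(1 − r²). Each row brings the d = 0.6 figure to or near the stated range, but moves the 0.51 SD figure away from 80%.

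**Step 4. Units.** If 0.51 means NRS points, d = 0.51/SD. The documents give no SD, so the SDs below are assumptions.

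| Assumed NRS SD (points) | Power for 0.51 points, 60 vs 60 | 0.51 SD in points |
|---|---|---|
| 1.5 | 46% | 0.77 |
| 2.0 | 28% | 1.02 |
| 2.5 | 20% | 1.28 |

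**Step 5. Target number.** Thirty divided by four arms is 7.5 per arm, so a main effect would compare about 15 vs 15. Power at 0.51 SD is then 27%, and 80% power needs 1.06 SD.

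**The case against.** The strongest reply is that the planned analysis is an ANCOVA adjusted for baseline. A 30 vs 30 contrast in the four-arm model, with about 115 error degrees of freedom, has 76% power at a baseline correlation of 0.50, 79% at 0.55 and 81% at 0.58. The inulin sentence is introduced as an additional statement, so it may come from a separate calculation, and the fair criticism would then be that an assumption went unreported. This does not rescue the sentence. It names a main effect, which is not 30 vs 30. The correlation appears nowhere, and the same adjustment would raise the adjacent 0.51 SD figure to about 89–93%.

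Several points do stand:

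- If the main effect is meant, power is understated, which is the safe direction, and the conclusion of adequate power is true.
- The planned 120 is unaffected.
- The missing SD unit is probably shorthand, since the paragraph gives its other pain effects in SDs. The floor of thirty has probably lost the words *per arm*. The low powers in steps 4 and 5 show what the literal text implies, not what the sponsor is likely to intend.
- The analysis plan explicitly describes a pooled comparison only for exercise against no exercise. A 60 vs 60 figure for inulin fits the sample size section's own description of the factorial comparison, but the matching inulin contrast should be named in the analysis plan.

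**Conclusion.** The concern holds. Under the convention that reproduces the plan's 80% for 0.51 SD (two-sided 0.05, no covariate adjustment, no dropout), the ~75–80% at d = 0.6 is wrong on either reading. It overstates power by 12 to 17 percentage points for 30 vs 30 (63%), or understates it by 10 to 15 points for the 60 vs 60 main effect (90%). Readings that reach the stated range need an unstated assumption that breaks the neighbouring figure.

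The missing SD unit and the two target numbers (at least thirty against 120) are genuine contradictions in the text, though probably slips. The main finding does not depend on them.

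This must be corrected because it concerns the stated power, target difference and sample size for the primary outcome. It does not call the size of 120 into question for main effects of about 0.52 SD or more.

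**What to change.** 1. In Sample Size and Justification, replace the power sentences with wording such as: *120 participants will be randomised, 30 per arm. Each main effect compares 60 vs 60 at two-sided alpha 0.05, giving 79% power for 0.51 SD (80% for 0.52 SD) and 90% for 0.60 SD. A pairwise 30 vs 30 comparison has 63% power for 0.60 SD and needs 0.74 SD for 80%. These figures take no credit for baseline adjustment and assume no dropout.* If the sponsor wants credit for the ANCOVA, state the baseline correlation and its source and apply it to every figure.
2. Replace the closing target with 0.51 SD of the NRS, and give its equivalent in points using the SD from the previous exercise trial.
3. In Randomisation and Blinding, change the number to at least thirty participants per arm, 120 in total.
4. In the Statistical Analysis Plan, name the pooled inulin against no-inulin contrast, so that the quoted main-effect power belongs to a defined analysis.

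The cost is wording only. The pairwise power becomes less favourable, and no additional participants are needed.

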The exercise intervention has been described in detail previously (Gohir et al 2021 PMID: 33620447). It is focused on a mixture of concentric and eccentric exercises with open and closed-chain movements, for strengthening the legs including the muscles around the hips and knee joints as well as exercises to improve balance. An open kinetic chain is defined as "a combination of successively arranged joints in which the terminal segments can move freely" (Karandikar et al 2011 PMID: 21871418), while closed chain exercises are those in which the proximal joints move while the distal portion of the extremities is in a stationary position (Karandikar et al 2011 PMID: 21871418). The programme also includes educational sessions covering the fundamentals of OA, its treatment, self-managing symptoms of OA and the benefits of maintaining a healthy lifestyle.

DIETARY INTERVENTION

Inulin fibre (20g) in powder form (commonly found in root vegetables such as chicory) will be randomly allocated to eligible participants in order to test specific effects on gut microbiome

composition and metabolic markers. Inulin is easily dissolvable in liquid and can be incorporated into the usual diet - by adding water, juice, smoothies, cereal, yogurt.

CONTROL PLACEBO GROUP

The control group will continue with routine self-management which is offered in the community setting and will be instructed to receive maltodextrin (10g) in powder form (commonly found in corn, potatoes, rice) which can be consumed by adding to breakfast cereal/ smoothie/ yogurt or drink of choice similar to inulin will serve as a control/placebo to compare the effects observed with inulin.

FOLLOW UP DURATION

Six weeks post-intervention.

RESEARCH ASSESSMENT

Following outcome measures will be assessed:

- Quantitative Sensory Testing – QST (Pressure pain threshold – PPT and Temporal summation – TS)
- SCFAs, EC, gut microbiome and inflammatory pain-related biomarkers
- Physical functioning (Time up and go test, 30-second sit to stand test)
- Grip strength
- Hospital Anxiety and Depression Scale (HADS)

DESCRIPTION OF INTERVENTION

The study will be communicated verbally and in writing to participants who have knee pain from OA. Participants who meet the study's eligibility requirements will sign an informed consent form and be randomly assigned to either the interventional groups or the control/placebo group.

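### The goal of linking serum-marker changes to pain changes is supported only by mean marker changes, and the planned correlations have no lead pair, error control, exploratory label or adjustment for arm

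*Combined protocol and SAP*

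**What the plan says.** Under Sample size and justification, the paragraph on secondary outcomes states that "a key goal of this study is to link changes in molecular markers in serum to changes in pain and other outcomes" and attaches "n=120, 60 per arm for the 2x2 intervention". Two illustrations for a circulating pain modulator follow. With inulin it moved "from 0.32 to 0.71 nmol/L; SD=0.61 after 6 weeks of inulin supplementation hence yielding an effect size of 0.62 STDs". For exercise the text reads: "It increased from 1.61-1.82 nmol/L; SD=0.31 yielding an effect size of 0.61 STDs with the exercise intervention". No expected correlation, detectable correlation or power for an association is given there or elsewhere.

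The Statistical analysis plan describes the association work in one sentence: "Secondary analyses (i.e., correlations between changes in SCFAs and changes in pain measures) will be conducted using the appropriate type of statistical test", with the choice resting on normality and Spearman's given as an example. Both sides of the pairing are plural. Research assessment lists "SCFAs, EC, gut microbiome and inflammatory pain-related biomarkers" and, for sensory testing, "Pressure pain threshold – PPT and Temporal summation – TS"; with the NRS that makes three pain measures. The Outcomes section separately lists changes in inflammatory markers and in serum SCFAs as secondary outcomes.

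The document contains no multiplicity rule, no named lead marker-pain pair, no exploratory label for these correlations and no statement that they will be adjusted for randomised arm.

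**The concern.** There are three gaps.

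- **The support does not match the goal.** A marker can rise by 0.6 SD on average in people whose individual rises are unrelated to their change in pain. A reader of the sample size section could take the linking goal to be covered when its sensitivity has not been stated.
- **There is no error control.** Several unadjusted change-on-change correlations feed a formal secondary objective about the molecular pathways of pain relief. A nominally significant pair could be reported as a mechanism.
- **There is no adjustment for arm.** If an intervention moves both marker and pain, pooling the arms produces a correlation even when, within each arm, the two changes are unrelated.

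**Working it through.** **Inputs from the document.** n=120, 60 per factorial margin; marker means and SDs as quoted; the 0.51 SD pain difference used for the primary power statement; three pain measures (NRS, PPT, TS).

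**Assumptions.** Two-sided 5% and 80% power for each correlation; 3 SCFAs, since the document gives no number; complete data unless stated.

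**1. The plan's own marker figures.**
- Inulin: (0.71 − 0.32)/0.61 = 0.39/0.61 = 0.64; stated 0.62. Rounding of the inputs can just explain this: 0.38/0.615 = 0.618.
- Exercise: (1.82 − 1.61)/0.31 = 0.21/0.31 = 0.68; stated 0.61. Rounding cannot explain this: the minimum is 0.20/0.315 = 0.635.

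Both should be checked against their source, but the point does not depend on them.

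**2. What those figures can support.** Taken as a between-margin difference (that is, assuming no change in the comparator), 0.62 SD at 60 v 60 gives about 92% power. That is a statement about marker response.

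**3. What they cannot support.** Simulated power of the correlation test at n=120, with the mean marker change held at 0.62 SD:

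| True r | Power |
|---|---|
| 0 | 5% |
| 0.20 | 59% |
| 0.30 | 92% |

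The mean change is the same in every row, so it does not fix the power.

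**4. Detectable correlation.** By Fisher z, r = tanh[(z_α/2 + z_0.80)/√(n − 3)], with √117 = 10.817.
- One pair: (1.960 + 0.842)/10.817 = 0.259, so r = 0.25.
- Nine tests, Bonferroni, α = 0.05/9 = 0.00556: (2.773 + 0.842)/10.817 = 0.334, so r = 0.32.
- Spearman (variance factor 1.06): 0.26 and 0.33.
- With 15% dropout (assumption, n=102): 0.27 and 0.35.
- Adjusting for arm with three indicator terms replaces n − 3 by n − 6: 0.26 and 0.33.

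Benjamini-Hochberg thresholds lie between the one-pair and Bonferroni values.

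**5. False links with no adjustment.** 3 × 3 = 9 null tests at 0.05.
- Expected number: 9 × 0.05 = 0.45, whether or not the tests are correlated.
- Chance of at least one, if independent: 1 − 0.95^9 = 0.37.
- Chance of at least one with illustrative correlations of 0.6 between SCFAs and 0.3 between pain measures: about 0.30 by simulation.

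**6. Correlation created by pooling arms.** Suppose one factor, 60 v 60, raises the marker by 0.62 SD and lowers pain by 0.51 SD, with no within-arm association.
- Covariance: 0.25 × 0.62 × (−0.51) = −0.079.
- Variances: 1 + 0.25 × 0.62² = 1.096 and 1 + 0.25 × 0.51² = 1.065.
- Pooled r = −0.079/√(1.096 × 1.065) = −0.07.
- Simulated rejection rate at nominal 5%: about 13%. After adjustment for the four arms it returns to about 5%.

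**The case against.** The strongest reply is that the paragraph is loosely worded and contains no wrong calculation. The mean changes sit under secondary outcomes, are introduced as an example and fit the listed marker-response outcomes. n=120 is justified by the NRS, and no power is claimed for a correlation. That stands: the figures have a proper use and should be reassigned, not deleted. What remains is that they directly follow the linking goal and nothing else supports it.

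A second reply is that these analyses are secondary, and conventions differ on whether such analyses need formal error control. This lowers the severity. It does not remove the point, because the goal is described as key and nothing marks the correlations as exploratory.

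Three stronger readings are tempting but not supported:
- **That every listed marker family will be correlated with pain, giving dozens of tests and a near-certain false link.** The only pairing named is "correlations between changes in SCFAs and changes in pain measures". The list in Research assessment is a list of measurements, the linking goal is limited to serum, and the microbiome is measured in faecal samples. No test count is given. On the 9-test assumption, a false link is a material risk but less likely than not.
- **That the trial is too small for the linking goal.** No target correlation is stated, so no shortfall can be shown; r of about 0.25 for a single pair is reasonable sensitivity.
- **That sensitivity should be judged in the 60 participants of the inulin arms.** The plan describes no such subgroup correlation.

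**Conclusion.** The point holds as a gap in justification and specification. The mean marker changes do not support the linking goal, and the planned correlations lack a lead pair, error control, an exploratory label and adjustment for arm. The error figures rest on the assumed 3 SCFAs and on all nulls being true. The 13% rejection rate rests on one factor moving both marker and pain by the sizes taken from the document. The detectable correlations rest on the full 120 being analysed. The primary NRS analysis does not depend on any of this, so severity is minor.

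**What to change.** Before any outcome data are seen, amend the SAP and the sample size section as follows:

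1. Keep the mean-change figures only as support for the marker-response secondary outcomes, after checking both effect sizes against their inputs.
2. For the linking goal, state the detectable correlation at n=120, two-sided 5%, 80% power: about 0.25 for one pre-named pair and about 0.32 across 9 tests (Bonferroni bound). Note that it is slightly higher for Spearman, with dropout or after arm adjustment, and replace 9 by the actual count.
3. Name one lead serum marker-pain pair, for example one serum SCFA with NRS change.
4. List the remaining marker-pain tests, apply Benjamini-Hochberg at 5% false discovery rate and report them as exploratory.
5. Estimate all associations adjusted for randomised arm, for example by partial correlation. False discovery control does not remove the correlation that pooling creates.

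The cost is wording only, with no added participants, visits or assays. The stated sensitivity becomes less favourable, and fewer nominal associations will be declared.
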